^b Subjects who discontinue taking study drug prematurely for any reason will undergo an ED Visit within 7 days of their last dose of study drug. In addition, Follow-Up Visits will be scheduled 4 and 12 weeks after the last dose of study drug (Visit 14 and Visit 15, respectively). Subjects who discontinue study drug before reaching 12 months of treatment will also be asked to return to the clinic for a 12 month clinical assessment and then again at 24 months. Subjects who discontinue treatment between 12 and 24 months of treatment will be asked to return to the clinic for a 24 month clinical assessment. Subjects who discontinue early from study drug are considered “on study” as long as they continue to return for their clinical assessments at 12 and 24 months as outlined above, at which efficacy (MMSE, CDR, ADAS- cog₁₄) and quality of life (EQ-5D, QOL-AD and Zarit’s Burden Interview) will be assessed along with concomitant medications and AEs. These 12 and 24 month clinical assessment visits do not need to be attended if they fall within 8 days (visit window) after the ED Visit or within ±8 days of either of the Follow-Up Visits (Visit 14 and Visit 15).

- ^c All subjects, regardless of whether they complete all 24 months of treatment or discontinue study drug prematurely, will complete 2 posttreatment Follow-Up Visits; one 4 weeks after the last dose of study drug and a second 12 weeks after the last dose of study drug (Visit 14 and Visit 15 respectively). If clinically indicated, more frequent safety assessments can be made as UNS assessments or visits during the posttreatment Follow-Up Period. Subjects who have a Grade 2 or greater lymphocytopenia (less than 800/mm³) during the follow-up period (ie., at either Visit 14 or Visit 15) should have ALC measured every 4 weeks until resolution or confirmation of a non drug-related cause of the lymphocytopenia. ALC will be derived from the complete blood count (CBC) with differential representing the normal lymphocytes (with atypical lymphocytes removed and presented as a separate count if they are present) and calculated by the white blood cell count × percentage of lymphocytes. (revised per Amendments 01 and 02) (revised per Amendments 01 and 02)

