- ⁿ The subject components of these assessments are to be completed in the morning whenever possible, or consistently at the same time of day. Ideally, the subject component of these assessments should be completed before more invasive assessments or procedures (eg, physical examination, ECG, blood draws). The FAQ is to be administered to the study partner. At visits where the CDR or FAQ are conducted, the investigator will determine whether the study partner must attend in person or whether telephone contact will be suitable, and will base this determination upon the functional ability of the subject among other factors.
- ^o Disease staging will be performed every 3 months. The site clinician is required to confirm the staging of disease, ie for subjects who were, at Screening, not clinically staged as dementia, does the subject still meet the definition of MCI due to AD or have they progressed into the stage of clinical dementia. This staging decision will be verified via a central review process and adjudicated if necessary. Adjudication will only occur when there is a discrepancy between the diagnosis and clinical disease staging made by the site compared to that determined by the central review process; moreover, where adjudication is required, it will be undertaken by an independent assessor(s). (revised per Amendment 01)
- ^p The clinical assessment of suicidality will require input from both the subject and the study partner
- ^q There are 3 separate administrations of the EQ-5D as follows: (1) in the subject by self report, (2) in the study partner by self report, (3) in the subject by proxy using the study partner (revised per Amendment 02)
- ^r There are 2 separate administrations of the QOL-AD as follows: (1) in the subject by self report, (2) in the subject by proxy using the study partner (revised per Amendment 02)
- ^s MRI scans are to include vMRI and fMRI sequences and will be read by an approved central reader. MRI imaging will be conducted on separate days from the scheduled visits. MRI imaging should be conducted within the 7 days before Visits 9 and 13. In the event of an Unscheduled Visit, the investigator in consultation with the Medical Monitor will determine whether or not a safety MRI should be conducted. If an ED Visit takes place, an MRI is to be conducted if not already performed during the preceding 90 days.

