9.5.5 Completion/Discontinuation of Subjects

A subject may elect to withdraw from the study at any time for any reason. All subjects who discontinue study drug early for any reason will undergo an ED Visit within 7 days of their

last dose of study drug (see [Section 9.1.2.2](#)). In addition, Follow-Up Visits will be scheduled 4 and 12 weeks after the last dose of study drug (Visit 14 and Visit 15, respectively) (see [Section 9.1.2.2](#)). These Follow-Up Visits will be conducted to monitor efficacy and safety parameters after early withdrawal from the study or discontinuation of study drug. See [Table 3](#) for full details of the assessments to be performed at these visits.

All subjects who discontinue study drug before reaching 12 months of treatment will also be asked to return to the clinic for a 12 month clinical assessment and then again at 24 months. Subjects who discontinued treatment between 12 and 24 months of treatment will be asked to return to the clinic for a 24 month clinical assessment. Subjects who discontinue early from study drug are considered “on study” as long as they continue to return for their clinical assessments at 12 and 24 months as outlined above, at which efficacy and quality of life will be assessed along with concomitant medications and AEs. However, subjects who discontinue study drug early are not considered to have ‘completed’ the study as a final Subject Disposition. A subject removed from the study for any reason may not be replaced.

The investigator will promptly explain to the subject involved that the study will be discontinued for that subject and provide appropriate medical treatment and other necessary measures for the subject. A subject who has ceased to return for visits will be followed up by mail, phone, or other means to gather information such as the reason for failure to return, the status of treatment compliance, the presence or absence of AEs, and clinical courses of signs and symptoms.

The primary reasons for early withdrawal from the study are: AE, lost to follow-up, subject choice, withdrawal of consent, pregnancy, study terminated by sponsor, and other. The secondary reasons for early withdrawal from the study are: AE, subject choice, and other.

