9.7.1.1.2 SECONDARY ENDPOINTS

The secondary endpoints of the study are:

- Time to worsening of CDR scores by 24 months (eg, the worsening of global CDR score is defined as an increase from baseline by at least 0.5 points on the global CDR scale on 2 consecutive scheduled visits at which global CDR is undertaken)
- Time to conversion to dementia for subjects who were not clinically staged as dementia at Baseline based on clinical diagnosis
- The rate of change over time (mean slope) based on CDR-SB score over 24 months
- Change from baseline in CDR-SB at 27 months (ie, 24 months of treatment plus 3 months posttreatment follow-up) (revised per Amendment 01)
- Change from baseline in ADAS-cog₁₄, MMSE, and FAQ at 24 months
- Change from baseline in ADAS-cog₁₄ Word List (immediate recall and delayed recall) at 24 months (revised per Amendment 01)

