9.7.1.6.1 PRIMARY EFFICACY ANALYSIS

The primary analysis will be based on an intent to treat philosophy without regard to adherence to treatment. The primary analysis of the change from baseline in CDR-SB at 24 months will be performed to compare elenbecestat (E2609) 50 mg per day versus placebo using a linear mixed effects model for repeated measures (MMRM) on the FAS. The MMRM model will include baseline CDR-SB as a covariate, with treatment group, visit, randomization stratification variables (ie, region [7 levels], clinical dementia [yes, no], and concurrent AD medication use at randomization (Visit 2) [yes, no]), and treatment group-by-visit interaction as fixed effects. (revised per Amendments 01 and 02) An unstructured covariance matrix will be employed to model the covariance of within subject effect; if MMRM fails to converge then a covariance structure with fewer parameters from the following list will be employed according to the prespecified order in the list until the MMRM converges. The list of covariance structure will include Heterogeneous Toeplitz, Toeplitz, Heterogeneous Compound Symmetry, and Compound Symmetry. This primary analysis will include all observed post baseline data of the change from baseline in CDR-SB without imputation of missing values. The treatment effect for elenbecestat (E2609) versus placebo will be compared at 24 months based on MMRM model. The LS means and difference in LS means between elenbecestat (E2609) treatment group and placebo, and corresponding 95% CI will be presented.

The null hypothesis is that there is no difference in the mean change from baseline in CDR-SB at 24 months between elenbecestat (E2609) 50 mg per day and placebo. The corresponding alternative hypothesis is that there is a difference in the mean change from baseline in CDR-SB at 24 months between elenbecestat (E2609) 50 mg per day and placebo.

The primary analysis will be repeated to minimize the impact of change in concomitant AD medications where efficacy data after initiation of new AD medications and increase of current AD medications will be censored.

The following sensitivity analysis will be conducted to evaluate the impact of missing data: the primary endpoint will be analyzed using ANCOVA after multiple imputation. The ANCOVA model will include baseline CDR-SB as a covariate, with treatment group and randomization stratification variables as factors.

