The other continuous secondary efficacy endpoints as defined above will be analyzed using the same MMRM model as the primary efficacy analysis to compare elenbecestat (E2609) 50 mg per day versus placebo on the FAS, using baseline value corresponding to the response variable in the model.

The relationship between clinical changes at 24 months (CDR-SB, ADAS-cog₁₄, MMSE, and FAQ) and changes in each of the biomarkers (amyloid PET, CSF t-tau and p-tau, vMRI, and fMRI) at 24 months, will be evaluated using an ANCOVA model. (revised per Amendment 01) Changes in clinical scales at 24 months will be the response variables and either continuous or categorical change of biomarkers will be independent variables. The ANCOVA model will also include baseline value for clinical scale as a covariate,

randomization stratification variables, treatment group as factors, and other terms as appropriate.

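### Table 3 footnote b leaves the FAQ and disease staging out of the 12- and 24-month visits of subjects who have stopped study drug, so two secondary endpoints have no scheduled data beyond 12 weeks after the last dose

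*Protocol*

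**What the plan says.** Subjects who stop before 12 months are asked back at 12 and 24 months; those who stop between 12 and 24 months are asked back at 24 months. Sections 9.3.3 and 9.5.5 describe these visits in general terms, as ones "at which efficacy and quality of life will be assessed along with concomitant medications and AEs". Table 3 footnote b is the only place that names instruments: "at which efficacy (MMSE, CDR, ADAS- cog₁₄) and quality of life (EQ-5D, QOL-AD and" the Zarit interview, plus concomitant medications and adverse events. It waives the visit if it falls within 8 days after the early discontinuation (ED) visit or within 8 days either side of Visit 14 or 15.

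Section 9.7.1.1.2 lists among the secondary endpoints "Change from baseline in ADAS-cog₁₄, MMSE, and FAQ at 24 months" and "Time to conversion to dementia for subjects who were not clinically staged as dementia at Baseline based on clinical diagnosis". Footnote o to Table 3 states: "Disease staging will be performed every 3 months". It makes no exception for subjects off drug.

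Under section 9.7.1.6.2, FAQ change on the FAS "will be analyzed using the same MMRM model as the primary efficacy analysis". Conversion is analysed by Cox regression on the FAS, censored at the last dementia diagnosis. Secondary endpoints are tested in sequence after the primary.

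**The concern.** Footnote b narrows the general word efficacy to three scales. The FAQ belongs to the efficacy assessments in section 9.5.1.3.1, and section 9.2.3 rates it above cognitive change as an indicator of clinical meaning. Three instruments that feed only exploratory endpoints (EQ-5D, QOL-AD, Zarit) are kept, while two assessments that feed secondary endpoints are left out.

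Followed as written, a subject who stops drug and attends month 24 contributes a 24-month CDR, MMSE and ADAS-cog14 but no FAQ. The same MMRM would then rest on observed late off-drug values for the cognitive scales. For FAQ it would rely on the model's missing-at-random assumption. The functional endpoint would have a different off-drug follow-up from the endpoints it should support.

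For conversion, the last scheduled diagnosis of an early stopper is at Visit 15, so censoring follows soon after the drug stops. That may be informative: inadequate therapeutic effect is a listed reason for stopping drug, and the stopping rules for rash, infection and lymphocytopenia could act differently in the two arms. No SAP can recover assessments that were never made.

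**Working it through.** **1. The plan's own figure.** Inputs from section 9.7.2: placebo change 1.75, SD 2.05, 25% reduction, 30% dropout, two-sided alpha 0.05, power 90%, 665 per arm.

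- Difference: 0.25 × 1.75 = 0.4375.
- Per arm: n = 2 × (1.960 + 1.282)² × 2.05² / 0.4375² ≈ 462.
- Inflated: 462 / 0.70 = 660 per arm, 1320 in total. The exact t-test gives 463, then 463 / 0.70 = 661.4, so 662 per arm.
- Power with 665 × 0.70 = 465.5 per arm: 0.902.

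The stated 1330 reproduces closely and is not in dispute. It concerns CDR-SB, which footnote b retains.

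**2. What is scheduled once drug has stopped** (Table 3 and footnote b).

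| Assessment | Endpoint level | ED | Visit 14 | Visit 15 | Off-drug 12/24 months |
|---|---|---|---|---|---|
| CDR | primary | yes | yes | yes | yes |
| MMSE, ADAS-cog14 | secondary | yes | yes | yes | yes |
| FAQ | secondary | yes | yes | yes | **not listed** |
| Disease staging | secondary (conversion) | yes | no | yes | **not listed** |
| EQ-5D, QOL-AD, Zarit | exploratory | yes | no | no | yes |
| NPI-10 | exploratory | yes | no | yes | not listed |

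**3. Who is affected.** Month 24 is week 104 and Visit 15 is 12 weeks after the last dose. A subject whose last dose is before about week 104 − 12 = 92 has no scheduled FAQ or staging at or near month 24.

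- Last dose at week 52: Visit 15 at week 64, then 104 − 64 = 40 weeks to month 24 with neither assessment.
- Last dose at week 26: Visit 15 at week 38, then 104 − 38 = 66 weeks, although the subject is asked to attend at both 12 and 24 months.

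A subject who stops after about week 92 has FAQ visits on both sides of month 24 or close to it.

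**4. How many.** The protocol gives no rate for stopping drug while staying on study. The 30% in section 9.7.2 does not separate the two, and the sample size calculation treats those subjects as contributing nothing at month 24. As an assumption, take 5% to 30%.

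- Month-24 attenders without an FAQ: 0.05 × 1330 ≈ 66, up to 0.30 × 1330 = 399.
- At risk of conversion: mild dementia is capped at about 25%, so at least about 0.75 × 1330 ≈ 998. Without scheduled staging after Visit 15: 0.05 × 998 ≈ 50, up to 0.30 × 998 ≈ 299.

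At each assumed rate these counts are upper limits. Some subjects will stop late, have the visit waived or not attend.

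**5. What cannot be computed.** The protocol gives no SD or effect for the FAQ and no conversion rate, so no loss of power follows for either endpoint.

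**The case against.** The strongest reply is that the data are truncated rather than absent. The FAQ is taken at ED and at 4 and 12 weeks after the last dose, and staging at ED and 12 weeks. The 24-month visit is waived only near visits at which the FAQ is done. If those values enter the MMRM, it goes too far to say that the FAQ estimates an effect as if subjects had stayed on drug. How they map to analysis visits is properly left to the SAP. This stands, and it limits the gap to the period beyond Visit 15. For staging the waiver is less complete, because staging is not marked at Visit 14.

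It can also be said that the footnote is a drafting slip, since the body text promises efficacy without limit and footnote o requires staging every 3 months. That is plausible. But footnote b is the only passage that names instruments, so it is what a site would follow.

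A reader might infer three stronger claims that the protocol does not support:

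- That the plan promises intent to treat for these endpoints. The sentence "The primary analysis will be based on an intent to treat philosophy without regard to adherence to treatment" covers the primary analysis only. For the secondary endpoints the plan gives the FAS, the model and the censoring rule.
- That the FAQ standard error rises by up to 20% (√(1330/931) = 1.195) or its effect is overstated by 1/0.7 = 1.43. Here 931 = 0.70 × 1330 is already the plan's working number for CDR-SB, so the first ratio does not isolate a loss due to footnote b. The second needs all 30% to stop drug, stay on study and attend, with all benefit lost off drug.
- That declining subjects stop more often. The protocol gives no rate by reason.

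**Conclusion.** The omission is real and stands in the current text of footnote b. For subjects who stop more than about 12 weeks before month 24, FAQ at 24 months and time to conversion to dementia have no scheduled data beyond Visit 15, unlike CDR, MMSE and ADAS-cog14. The footnote conflicts with footnote o and sits badly with sections 9.3.3 and 9.5.5. The resulting censoring of conversion may be informative; the protocol does not show that it is.

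The counts in the working rest on an assumed 5% to 30% stopping drug but staying on study; no bias or power figure can be attached to them. The primary endpoint and its sample size are untouched, and both secondary endpoints are tested only if the primary succeeds. This should be fixed, but it does not threaten the main conclusion of the trial.

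**What to change.** In Table 3 footnote b, add the FAQ, and disease staging for subjects not staged as demented at baseline, to the 12- and 24-month off-drug visits. Refer to that list in sections 9.3.3 and 9.5.5 so that the word efficacy has one meaning. In footnote o, say what staging applies off drug: two annual visits cannot deliver a 3-monthly schedule, so the exception should be explicit. NPI-10 could be added at the same time, but it is exploratory and incidental here.

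The cost is a short amendment, slightly longer visits and some additional central staging reviews, with adjudication where site and central review disagree. The study partner, who answers the FAQ, already contributes to the CDR and the Zarit interview at these visits, in person or by telephone. The change helps only visits still to come, so it is worth making early.

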Urine pregnancy test (females of CBP only) ^k	X		X	X	X	X	X	X	X	X	X	X	X	X			X
Blood sample for viral characterization ^l	X																
Blood sample for storage for immune status ^m	X		X		X	X		X				X	X	X	X	X	X

Table 3 Schedule of Procedures/Assessments in Study E2609-G000-301

Phase	Randomization															UNS Visit ^d
	Treatment													Follow-Up		
Period	2	3	4	5	6	7	8	9	10	11	12	13	ED ^b	14 ^c	15 ^c	
Visit ^a																
Day	1	15	29	57	85	183	274	365	456	547	638	729		757	813	
Week	1	3	5	9	13	27	40	53	66	79	92	105		109	117	
Weeks elapsed since 1st dose	0	2	4	8	12	26	39	52	65	78	91	104		108	116	
Nominal months elapsed since 1st dose	0		1	2	3	6	9	12	15	18	21	24		25	27	
Procedures/ Assessments																
MMSE ⁿ	X					X		X		X		X	X	X	X	
CDR ⁿ	X				X	X	X	X	X	X	X	X	X	X	X	
ADAS-cog ₁₄ ⁿ	X					X		X		X		X	X	X	X	
FAQ ⁿ	X					X		X		X		X	X	X	X	
Disease Staging ^o					X	X	X	X	X	X	X	X	X		X	
NPI ₁₀	X					X		X		X		X	X		X	
C-SSRS	X											X	X			
Clinical assessment of suicidal thinking and behavior ^p		X	X	X	X	X	X	X	X	X	X			X	X	X
EQ-5D ^q						X		X		X		X	X			
QOL-AD ^r						X		X		X		X	X			
Zarit's Burden Interview of study partner						X		X		X		X	X			
MRI including vMRI and fMRI ^s								X				X	X			
Amyloid PET (optional substudy) ^t								X				X	X			
Telephone contact ^u		X	X		X	X		X		X		X	X			
Blood samples for PK ^v		X	X		X	X		X		X		X	X			
Blood samples for PD and other biomarkers ^w		X	X		X	X		X		X		X	X	X	X	
CSF sampling for PK and PD (optional)												X	X			

Table 3 Schedule of Procedures/Assessments in Study E2609-G000-301

Phase	Randomization															UN Visit ^d
	Treatment													Follow-Up		
Period	2	3	4	5	6	7	8	9	10	11	12	13	ED ^b	14 ^c	15 ^c	
Visit ^a																
Day	1	15	29	57	85	183	274	365	456	547	638	729		757	813	
Week	1	3	5	9	13	27	40	53	66	79	92	105		109	117	
Weeks elapsed since 1st dose	0	2	4	8	12	26	39	52	65	78	91	104		108	116	
Nominal months elapsed since 1st dose	0		1	2	3	6	9	12	15	18	21	24		25	27	
Procedures/ Assessments substudy) ^x																
Adverse events	X	X	X	X	X	X	X	X	X	X	X	X	X	X	X	X
Sleep/Dream Questionnaire ^y	X	X	X	X	X	X	X	X	X	X	X	X	X	X	X	X
Possible Drug Abuse Potential Form/ Questionnaire ^z	X	X	X	X	X	X	X	X	X	X	X	X	X	X	X	X
Randomization	X															
Dispense study drug	X ^{aa}	X	X	X	X	X	X	X	X	X	X					

Notes:

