ADAS-cog₁₄ = Alzheimer’s Disease Assessment Scale - Cognitive subscale (14 items), CBP = child-bearing potential, CDR = Clinical Dementia Rating scale, CMV = cytomegalovirus, CNS = central nervous system, CSF = cerebrospinal fluid, C-SSRS = Columbia Suicide Severity Rating Scale, ECG = electrocardiogram, ED = Early Discontinuation, EQ-5D = EuroQol-5 Dimensions, FAQ = Functional Assessment Questionnaire (also known as the Functional Activities Questionnaire), fMRI = functional MRI (to be performed task free at resting state), HSV1 = herpes simplex virus 1 (orolabial herpes), HSV2 = herpes simplex virus 2 (genital herpes), INR = International Normalized Ratio, LP = lumbar puncture, MMSE = Mini Mental State Examination, MRI = magnetic resonance imaging, NPI = Neuropsychiatric Inventory, PBMC = peripheral blood mononuclear cell, PD = pharmacodynamics, PET = positron emission tomography, PK = pharmacokinetics, QOL-AD = Quality of Life in Alzheimer’s Disease, UNS = unscheduled, vMRI = volumetric MRI.

^a A window of ±3 days will be permitted for Visits 3 and 4. A window of ±7 days will be permitted for Visits 5 and 6. A window of ±10 days will be permitted for Visit 7 to 13 inclusive. A window of ±3 days will be permitted for the Follow-Up Visits. If use is made of the permitted visit windows, every effort should be made to bring the subject back in line with the “weeks elapsed since 1st dose” at subsequent visits.

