9.7.1.1.3 EXPLORATORY ENDPOINTS

The exploratory endpoints of the study are:

- Time to change of concomitant AD treatment (ie, dose increase and/or initiation of treatment with AChEI or memantine after randomization) by 24 months
- The proportion of subjects at 24 months who received dose increases and/or initiation of treatment with AChEI or memantine after randomization
- The rate of change over time (mean slope) based on NPI-10 item score over 24 months
- Change from baseline in NPI-10 item at 24 months

- Change from baseline in EQ-5D (subject self-reported, study partner self-reported, and subject measured by proxy) and QOL-AD (subject and study partner) at 24 months
- Change from baseline in Zarit's Burden Interview at 24 months

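### Early stoppers may skip the 24-month assessment when Visit 14 or 15 falls within 8 days of it, but EQ-5D, QOL-AD and Zarit are not scheduled at those visits

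*Protocol*

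**What the plan says.** All references are to the current (Amendment 03) protocol text.

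- **What is promised.** Footnote b of Table 3 (Section 9.5.2.1) brings early stoppers back at months 12 and 24, or at month 24 only if they stop after month 12. Besides MMSE, CDR and ADAS-cog14, it says of these visits that "quality of life (EQ-5D, QOL-AD and Zarit’s Burden Interview) will be assessed along with concomitant medications and AEs". Sections 9.3.3 and 9.5.5 repeat that efficacy and quality of life are assessed then.
- **What is waived.** The same footnote excuses attendance in two cases. The first is closeness to the early discontinuation visit: "These 12 and 24 month clinical assessment visits do not need to be attended if they fall within 8 days (visit window) after the ED". The second, which is the one at issue here, is closeness to a Follow-Up Visit: "or within ±8 days of either of the Follow-Up Visits (Visit 14 and Visit 15").
- **When the nearby visits occur.** Early stoppers "will undergo an ED Visit within 7 days of their last dose of study drug". As for the later contacts, the footnote says that "Follow-Up Visits will be scheduled 4 and 12 weeks after the last dose of study drug (Visit 14 and Visit 15, respectively").
- **What those visits contain.** Table 3 marks MMSE, CDR, ADAS-cog14 and FAQ at ED, Visit 14 and Visit 15. The rows for EQ-5D, QOL-AD and "Zarit's Burden Interview of study partner" are marked at Visits 7, 9, 11, 13 and ED, and are blank at Visits 14 and 15. Section 9.5.5 refers to Table 3 for the content of the ED and Follow-Up Visits.
- **What uses the data.** The exploratory endpoints in Section 9.7.1.1.3 include 24-month change in EQ-5D and QOL-AD, and "Change from baseline in Zarit's Burden Interview at 24 months".

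**The concern.** The waiver makes sense only if the nearby visit stands in for the one that is skipped. For the ED Visit it does, because all the instruments are scheduled there. For Visits 14 and 15 it works for cognition and function but not for quality of life or study-partner burden. A subject can thus be in the clinic on the very day that month 24 falls due and have a CDR taken, while none of the three EQ-5D, two QOL-AD and one Zarit administrations is called for.

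At stake are avoidable missing 24-month values on listed endpoints, all of them in subjects who are off drug but still attending. This is a collection rule, so a statistical analysis plan cannot repair it: it can impute a score or map an earlier one, but it cannot recover one that was never taken.

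**Working it through.** **Inputs.** From Table 3: month 12 is Day 365, month 24 is Day 729 (728 days after first dose), Visit 14 is last dose + 28 days, and Visit 15 is last dose + 84 days. From footnote b: waiver tolerance ±8 days, ED within 7 days of last dose. From Section 9.7.2: 1330 subjects and 30% dropout.

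**The plan's own figure.** The 1330 serves here only as a denominator, but it reproduces. The difference is 0.25 × 1.75 = 0.4375 with SD 2.05, 90% power and 2-sided 0.05. The normal approximation gives 462 per arm, and 462/0.7 = 660. The t-test gives 463, and 463/0.7 = 661.4, so 662. The stated 665 per arm is consistent (power 0.902 at 665 × 0.7 per arm).

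**Last-dose days that trigger the 24-month waiver** (nominal schedule):

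- Through Visit 14: 729 − 28 ± 8, which is Days 693 to 709 (17 days).
- Through Visit 15: 729 − 84 ± 8, which is Days 637 to 653 (17 days).
- The bands do not overlap: 34 days in total.

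**Example.** Last dose on Day 645 puts Visit 15 on Day 645 + 84 = 729. The month-24 visit may be skipped, CDR is collected at Visit 15, and no questionnaire is scheduled.

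**Nearest available score.** ED takes place 0 to 7 days after last dose and includes all three instruments. It precedes the replacing visit by 21 to 28 days (Visit 14 band, 3-4 weeks) or 77 to 84 days (Visit 15 band, 11-12 weeks). Even in the most favourable case, last dose on Day 709 and ED on Day 716, the score is 729 − 716 = 13 days before month 24. For comparison, the on-treatment visit rule reads: "A window of ±10 days will be permitted for Visit 7 to 13 inclusive". So the ED score always lies outside the window used for Visit 13.

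**How many subjects.** Assume that a fraction *p* of the 1330 stop drug early, remain on study, and stop uniformly over 728 days. The number affected at month 24 is *p* × 1330 × 34/728, and 34/728 = 4.7%.

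| *p* | Early stoppers | Affected at month 24 | Share of 1330 |
|---|---|---|---|
| 20% | 266 | 12.4 | 0.9% |
| 30% | 399 | 18.6 | 1.4% |
| 40% | 532 | 24.8 | 1.9% |

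**Month 12.** The corresponding bands are Days 329-345 (365 − 28 ± 8) and Days 273-289 (365 − 84 ± 8), again 34 days and about 19 subjects at *p* = 30%. These subjects are still asked back at month 24, so they miss only the 12-month score.

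**The case against.** The strongest reply is that the waiver is permissive. It excuses attendance and does not say that the assessments are dropped. The same footnote promises quality of life at months 12 and 24, and Sections 9.3.3 and 9.5.5 ask early stoppers to return without mentioning any waiver. A site could hold the visit anyway, or add the questionnaires to Visit 14 or 15. This stands as a limit: a reader might infer that the rule forbids collection or makes the loss certain, and the text does not say so. But nothing requires the questionnaires either, and Section 9.5.5 points to a table that omits them.

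Second, a reader might add both time points and report about 37 subjects (2.8%). That would overstate the effect. The endpoints are change at 24 months, and the month-12 half lose no endpoint value.

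Third, the 30% in Section 9.7.2 is a dropout rate used for sample size, not a rate of stopping drug while staying on study. Subjects who leave the study attend neither visit and lose nothing through the waiver. This stands, and it is why a range is shown; the true figure could lie outside it.

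Fourth, an ED score exists, and an analysis plan might assign it to month 24. This helps somewhat in the Visit 14 band and little in the Visit 15 band; in neither is it a 24-month measurement. The ED arm of the waiver itself loses nothing.

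Last, a reader might infer bias or damage to the trial's main conclusion. The documents do not support that. The rule is the same in both arms, the endpoints are exploratory, and CDR is scheduled at both Follow-Up Visits.

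**Conclusion.** The gap is real but small. Followed exactly, Table 3 and its footnote b leave the 24-month EQ-5D, QOL-AD and Zarit not required for subjects whose last dose falls on about Days 637-653 or 693-709, although they attend a visit close to month 24. The size is about 19 of 1330 subjects (1.4%), or 12 to 25 for early-stop rates of 20% to 40%. It rests on uniform stopping times, on all early stoppers staying on study, on nominal visit days and on sites using the waiver. A similar number would miss only a 12-month score. The primary analysis is untouched, and no conclusion of the trial turns on this. It is worth correcting because the missing values are avoidable, fall entirely in off-drug subjects who attend anyway, and cannot be recovered at analysis.

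**What to change.** Add one sentence to footnote b: when Visit 14 or Visit 15 replaces the 12- or 24-month assessment, EQ-5D, QOL-AD and Zarit's Burden Interview are completed at that visit and assigned to month 12 or 24. Study-partner input may be given by telephone where the investigator finds it suitable, as Section 9.5.1.6 already allows. A matching conditional mark in the Visit 14 and 15 columns of Table 3 would keep table and footnote in step.

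The cost is the amended wording and three questionnaires at a visit that a small number of subjects already attend. Withdrawing the Follow-Up Visit arm of the waiver would also close the gap, but at the price of an extra visit for those subjects.
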